5.2 EXCLUSION CRITERIA

An individual who meets any of the following criteria will be excluded from participation in this study:

Exclusion Criteria (Medical):

- 1) Hb A1c greater than 8%

- 2) Patients who are currently taking either Insulin or Sulfonylureas (medication changes are allowed)
- 3) Prior history of gastric, pancreatic, hepatic, and/or splenic surgery
- 4) Prior radiation therapy to the upper abdomen
- 5) Prior embolization to the stomach, spleen, or liver
- 6) Cirrhosis
- 7) Known portal venous hypertension
- 8) Active peptic ulcer disease
- 9) Significant risk factors for peptic ulcer disease, including daily NSAID use
- 10) Large hiatal hernia, defined as >5 cm in size
- 11) Active H. pylori infection
- 12) Known aortic pathology, such as aneurysm or dissection
- 13) Renal insufficiency, as evidenced by an estimated glomerular filtration rate of <60 mL/min
- 14) Major comorbidity, such as active cancer, significant cardiovascular disease, or peripheral arterial disease
- 15) Pregnancy
- 16) Pre-existing chronic abdominal pain
- 17) Positive stool occult blood study
- 18) GI bleeding or bleeding diathesis within 5 years
- 19) Weight loss (intentional or unintentional) of more than or equal to 5% of body weight in the 6 months prior to randomization
- 20) A weight loss greater than 6lb during the weight management run-in
- 21) Use of anti-obesity medications in the 12 months prior to screening.
- 22)
- 23) Endoscopic findings that would preclude BAE (at the discretion of the study team)
- 24) History of gastric motility disorders or an abnormal nuclear gastric motility examination (to be performed in diabetic subjects only)
- 25) ASA Class 4 or 5 (very high risk surgical candidates: class 4=incapacitating disease that is a constant threat to life) at the time of screening for enrollment into the study – this exclusion criterion exists, because of the possibility that surgical intervention will be needed if the study intervention subsequently leads to severe adverse effects
- 26) Inflammatory bowel disease
- 27) Autoimmune disease or HIV+
- 28) History of allergy to iodinated contrast media
- 29) Failure to comply with pre-procedure weight management “run-in”, or other pre-procedural visits (specifically, participants must complete 80% of weight management and Lose It! Food tracking, and 100% of one-time visits, i.e. MRI, CTA, endoscopy)
- 30) Applicability of any contraindication regarding patient’s vasculature as per Instruction for Use
- 31) Inability to have an MRI scan (i.e., metal implants or claustrophobia)
- 32) Smokers/vapers/tobacco use
- 33) Active or new-onset endocrine disorders other than diabetes (stable disease acceptable)
- 34) Other unforeseen conditions that may make patients unsuitable for the procedure (study team discretion)

Exclusion Criteria (Psychiatric):

- 35) As determined by clinical judgment based on Clinical Interview, psychological/behavioral measures, medical records, previous mental health records/other collateral information (as available) and consistent with DSM -5 criteria:

36) Diagnosis of severe mental illness (i.e., chronic psychotic spectrum disorders, clinically significant mood disorders) AND/OR one or more of the following:

- Evidence of active relapse or active impairing symptoms (e.g., suicidal ideation, audio or visual hallucinations, paranoia, thought disturbance, severe impairment)
- Evidence of minimal supports or limited adherence to ongoing mental health care
- Failure to provide comprehensive aftercare plan that includes emergency plan for addressing future mental health relapse
- History of treatment refractory mental illness/recurrent relapse (multiple suicide attempts or inpatient psychiatric hospitalizations in the past 5 years)
- Within past 3 years: Inpatient psychiatric hospitalization
- Within past 5 years: Suicide attempt
- Declining to provide mental health records, a letter of support from mental health professionals, or consent for verbal consultation with mental health professionals when determined to be essential to evaluation.
- Cognitive impairment, if judged to have
- Limited capacity to make informed decision about procedure and inability to verbalize an understanding of the surgical procedure, risks and benefits.
- Inability to demonstrate an understanding of the permanency of lifestyle change required
- History of Anorexia or History of/Active Bulimia: If determined to be of low enough severity not to be a clear contraindication, minimum of 5 years abstinence from bulimia; current moderate to severe binge eating or night eating syndrome
- Active or History of Substance Abuse with less than 5 years of abstinence
- Current use of tricyclic anti-depressants or steroids, psychiatric medications associated with weight gain

5.3 LIFESTYLE CONSIDERATIONS

During this study, participants are asked to:

- Undergo medical therapy consisting of lifestyle counseling and weight management.
- Diabetic subjects will have their medications managed by their diabetes specialist, per routine care, as defined by American Diabetes Association guidelines.
- Eat nothing after midnight prior to their clinic visits.
- Agree to use birth control for the duration of the study (women of fertile age).
- Avoid use of tobacco products for the duration of the study.

5.4 SCREEN FAILURES

Screen failures are defined as participants who consent to participate in the clinical trial but are not subsequently randomly assigned to the study intervention or entered in the study. A minimal set of screen failure information is required to ensure transparent reporting of screen failure participants, to meet the Consolidated Standards of Reporting Trials (CONSORT) publishing requirements and to respond to queries from regulatory authorities. Minimal information includes demography, screen failure details, eligibility criteria, and any serious adverse event (SAE).

Individuals who do not meet the criteria for participation in this trial (screen failure) because of medications or other modifiable conditions (including but not limited to weight changes, non-cancerous failed endoscopy, active H. Pylori infection, uncontrolled glucose) may be rescreened. Rescreened participants should be assigned the same participant number as for the initial screening.

5.5 STRATEGIES FOR RECRUITMENT AND RETENTION

The targeted patient cohort is men and women aged between 21 and 70 years of various racial and ethnic backgrounds. Vulnerable patients (pregnant women, those who lack consent capacity, prisoners, children, employees, etc.) will be excluded as per the inclusion and exclusion criteria.

It is anticipated that approximately 1300 patients will be pre-screened to enroll 59 eligible subjects (based on prior experience in the BEAT Obesity trial) over a 24-month period. All subjects will be enrolled at the Johns Hopkins Hospital. Pre-screening will utilize an existing registry of patients from previous trials and patient referrals (weight management clinic referrals and self-referrals from advertising campaign). Identified or referred patients will be screened by phone using a telephone script.

Subjects will be followed for a period of 12 months. Retention strategies will include collecting multiple methods for contacting each participant and visit reminders. Subjects will receive payments of up to \$945 after the bariatric embolization (or control) procedure per the 12-month period, using the payment scheme tabulated below. Payment is given at 5 different intervals. Each test or log must be completed within the allotted range in order to receive payment. Payment may be prorated for weight management visits. For example, if a participant attended 4 weight management visits instead of 5 during weeks 4-8, they may receive \$40 during that time.

| Weeks 1-3 | Weeks 4-8 | Months 3-5 | Months 6-11 | Month 12 |
|------------------------------------|------------------------------------|------------------------------------|------------------------------------|----------------------------------|
| Food Log \$30 | Food Log \$20 | Food Log \$20 | Food Log \$30 | Food Log \$40 |
| Hunger Satiety \$30 | Hunger Satiety \$20 | Hunger Satiety \$20 | Hunger Satiety \$30 | Hunger Satiety \$50 |
| Hormone Test \$20 | Hormone Test \$30 | Hormone Test \$35 | Hormone Test \$40 | Hormone Test \$50 |
| | | MRI \$45 | MRI \$50 | MRI \$50 |
| | | Endoscopy \$70 | | |
| Weight Mgmt. (3 visits) \$40 | Weight Mgmt. (5 visits) \$50 | Weight Mgmt. (6 visits) \$55 | Weight Mgmt. (7 visits) \$60 | Weight Mgmt. (1 visit) \$5 |
| Blood Tests \$10 | Blood Tests \$10 | Blood Tests \$10 | Blood Tests \$10 | Blood Tests \$15 |
| Total \$130 | Total \$130 | Total \$255 | Total \$220 | Total \$210 |

Subjects who meet the entrance criteria will provide informed consent before being enrolled into the study. Consent will be obtained at the first visit at the Weight Management Center or Interventional Radiology. Participants will have as much time as necessary for giving consent.

Participants will have the study processes and consent form explained in detail, and then will be given time to read through the consent form. Participants will not be allowed to sign the consent form without reading through it first. Participants will be given the consent form in private; and probed for any potential questions they may have. A copy of the signed informed consent will be maintained and available for review by the Sponsor and designated monitor.

6 STUDY INTERVENTION

6.1 STUDY INTERVENTION(S) ADMINISTRATION

6.1.1 STUDY INTERVENTION DESCRIPTION

This study is being conducted under IDE G190208 utilizing an investigational device, BTG-001933, which is a radiopaque embolic bead 100-200 µm (Biocompatibles UK, Ltd) intended to be used for bariatric embolization [of the left gastric and/or gastroepiploic arteries](#). The summary of test validation studies is on file with the FDA and available in the Investigator's Brochure.

Control Arm Procedures

Participants randomized to the control arm will follow the same screening and pre-procedure assessment, and will also take the same pre-procedure medications. After becoming eligible, participants will be scheduled for their procedure. On procedure day, the interventional radiologist will determine radial or groin access in the post-anesthesia care unit per local policy. After the participant and procedure area are prepped, and a basic tray is opened, all participants will be given standard moderate sedation medications. At this point, the participant will have a drape placed over a drape support above their face to limit their vision and be given ear plugs and noise-cancelling headphones to dampen their hearing, preventing them from seeing and hearing the procedure but still allowing them to keep in contact with the procedure team. The participant will be randomized to either the control or intervention arm using central randomization software. Participants randomized to the control arm will receive no other procedural intervention. The procedural team instead will follow a prescribed simulated protocol that will mimic an actual embolization procedure. All participants will receive subcutaneous lidocaine and a skin nick to their groin or their wrist as pre-determined by the operating physician in the pre-anesthesia care unit, including those randomized to the control arm. If the skin nick is on the wrist, the operating physician will close it with an external compression device, and if it is in the groin, the physician will hold pressure for at least 5 minutes.

All procedure images and reports, regardless of the randomization arm, will be kept with the unblinded member of the study team, and will not be housed centrally. All participants will adhere to the same follow-up schedule, meeting with blinded members of the study team only. The procedural team will not have further contact with the participant, the participant will only be followed by the blinded study team. Once the study is closed, all reports and images will be entered into the clinical record.

Bariatric Embolization Procedure

The bariatric embolization procedure will be performed under moderate sedation by experienced interventional radiologists. This procedure will take about one-and-a-half to three hours. The manufacturer's Instruction for Use will be followed for the procedure.

The participant will be placed on the X-ray fluoroscopy table. Radial or femoral vascular access will be achieved using a small 21-gauge needle, then dilated serially over a guidewire to accommodate a 5 French vascular sheath(23). The participant will receive local anesthesia in the skin of their leg or wrist, then a different small catheter will be placed through the participant's skin into an artery that leads to the participant's abdomen.

Using standard catheters, 3-dimensional imaging will be acquired of the stomach, the arteries supplying the fundus arising off the celiac vessel will be selected. Then, a microcatheter will be advanced into the left gastric and/or gastroepiploic arteries supplying the fundus and small calibrated spheres (100-200 μm size [BTG-001933]) will be infused until stasis of anterograde arterial flow is achieved, with particular care to avoid infusion of non-target arteries. Only the left gastric and/or gastroepiploic arteries will be embolized. Stasis will be defined as visualization of contrast within the target artery for at least 5 cardiac cycles.

Upon completion, repeat 3-dimensional imaging will be acquired to assess bead distribution and fundal coverage. Following this the catheters will be removed and hemostasis will be achieved with manual compression or a closure device.

The participant will be monitored in the post-sedation recovery room until the participant meets the usual admission criteria, per local policy, followed by an overnight hospital admission for observation. During observation, intravenous fluids will be given to ensure adequate hydration status. If necessary, participants will be given analgesics, anti-nausea, and anti-emetic medication. If the participant continues to display pain, nausea, vomiting, etc., the participant may be kept in hospital for up to 48 hours post-procedure. The participant will be asked to avoid exertion for 48 hours following the procedure. Participants will adhere to a written post procedure diet plan consisting of a slow advancement from clear liquids, progressing to full liquids and finally solids. At which point they will be advanced to a regular diet as directed by the Weight Management Center. Please see post procedure diet plan in Appendix A.

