4.2 SCIENTIFIC RATIONALE FOR STUDY DESIGN

Due to the psychological basis for weight loss, a sham control procedure is required for comparison. All patients will receive weight management support, which is routine care for this patient population.

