8.2.3 History & Physical

Medical history deemed clinically significant, relevant to the clinical trial objectives and design, will be collected per body system (allergy/immunology), auditory/ear, blood/bone marrow, cardiac arrhythmia, cardiac general, dermatology/skin), endocrine metabolic, gastrointestinal, hemorrhage/bleeding, hepatobiliary/pancreatic, infection, musculoskeletal/soft tissue, neurologic, ocular/vision, psychiatric, pulmonary/upper respiratory, renal/genitourinary, sexual reproductive function, vascular).

The use of concurrent medications (medications taken within 30 days of screening and during the conduct of the study) will be obtained and documented in source documentation and on the relevant eCRF.

All ongoing medical conditions and adverse events arising from treatment of those conditions present for 30 days or more are generally considered a part of the patient's baseline medical history and must be recorded where indicated.

A full physical examination, including actual measured height (required at screening only) and actual scale measured weight, will be performed by a qualified licensed individual. A review of body systems will include the following:

- Waist circumference
- General appearance, overall well-being and functional capacity
- Skin
- Head, Ears, Eyes, Nose, Throat (HEENT)
- Respiratory
- Cardiovascular
- Abdomen (including liver, gastrointestinal system)
- Musculoskeletal, extremities and mobility
- Neurological
- Vital signs: Assessments of vital signs (e.g., blood pressure, heart rate, temperature) will be performed at all study visits. When possible, blood pressure and heart rate will be determined after the patient has been in the sitting position for 5 minutes. Respiratory rate will only be obtained at baseline (i.e. at the weight management intake visit during screening).

A full physical examination as detailed above will be performed at baseline (weight management screening intake visit), 1-week, 2-weeks, and 1-month post-procedure. Vital signs, including weight, will be taken at all visits with weight management, however, waist circumference will only be measured at the weight management intake visit (screening period), on procedure day, and at the 1-month, 3-month, 6-month, and 12-month post-procedure weight management follow-up visits.

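### For groin access the protocol allows a closure device after embolization but gives only held pressure in the control-arm text, and nothing requires the observable access site to match between arms, so the site could give a clue to allocation.

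*Protocol*

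**What the plan says.** Protocol 6.1.1 treats closure under two subheadings.

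- **Control Arm Procedures.** A sentence covering both arms comes first: "All participants will receive subcutaneous lidocaine and a skin nick to their groin or their wrist as pre-determined by the operating physician". The closure rule comes next. A nick at the wrist is closed by a device that applies compression from outside. For the other site the text reads: "if it is in the groin, the physician will hold pressure for at least 5 minutes". The control team otherwise "will follow a prescribed simulated protocol that will mimic an actual embolization procedure"; the content of that simulation is not given.
- **Bariatric Embolization Procedure.** Radial or femoral arterial access is "dilated serially over a guidewire to accommodate a 5 French vascular sheath". At the end, "hemostasis will be achieved with manual compression or a closure device". There is no split by site, no device type and no minimum holding time.

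The same section and 6.3 say that after the procedure participants meet only blinded staff. Section 8.2.3 schedules full physical examinations at "1-week, 2-weeks, and 1-month post-procedure" and lists skin among the items reviewed. SAP 3.3 says the team evaluating patients afterwards will not know which procedure was done. SAP 3.1 repeats the skin nick for controls but says nothing about closure.

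Protocol 4.2 gives the reason for the sham: "Due to the psychological basis for weight loss, a sham control procedure is required for comparison".

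**The concern.** The drape, ear plugs and headphones described in 6.1.1 and 6.3 work only while the procedure is under way. The access site can still be observed afterwards, during the overnight admission and at the early examinations. If a closure method or dressing can occur after embolization but not after sham, it is a cue that depends on the arm and comes from the protocol's own wording.

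The primary endpoint is 12-month weight change under a counseling program, so it depends on diet and adherence. A participant or counselor who suspects the allocation may behave differently. If suspicion of active treatment increases effort, the between-arm difference moves toward BAE. This is the influence the sham is meant to remove.

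**Working it through.** **Step 1. Set the texts side by side.**

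| Site | Control-arm text | Embolization text |
|---|---|---|
| Wrist | External compression device | Manual compression or a closure device, site not specified |
| Groin | Held pressure, at least 5 minutes | The same sentence, site not specified |

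At the wrist both texts admit a device, so device use there does not separate the arms. At the groin the control-arm text has pressure only, while the embolization text does not exclude a device.

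**Step 2. Try each reading.**

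- *The control-arm rule covers everyone.* The all-participants sentence just before it supports this. The embolization text then conflicts with it at the groin.
- *The control-arm rule covers controls only.* The subheading supports this. A groin device is then permitted in one arm and not provided for in the other.
- *The embolization sentence is an unsplit summary of the same two methods*, device at the wrist and hand pressure at the groin. Nothing then differs by arm, but the text does not say so and leaves a groin device open.

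The first two readings need reconciliation and the third needs clarification.

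**Step 3. Look for a safeguard elsewhere.** No text in either document requires matched closure, matched dressing or concealment of the site. The safeguards that exist are:

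- The unseen simulation script, which may cover closure.
- The guess surveys: the Schedule of Activities marks them at 4 weeks and 12 months, and 6.3 describes them for team and subjects. They detect unblinding after it has happened.
- The check of procedural matters, including blinding, after the pilot patients (9.4.6). As worded, those patients all undergo embolization, so it cannot compare closure between arms.

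**Step 4. Size.** The documents give no rate of groin access, device use, visible signs or recognition, so no bias can be derived. What can be shown is how sensitive the planned test would be to an assumed bias.

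Inputs from Protocol 9.2 and SAP 3.8: SD 7 kg, difference 8 − 3.3 = 4.7 kg, two-sided alpha 0.2, 21 evaluable per arm. The stated sample size reproduces: the normal approximation gives 20 per arm, the t distribution gives 21 with 80.9% power, and 21/0.8 = 26.25 rounds up to 27. The sample size is not in dispute.

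- Standard error = 7 × √(2/21) = 2.16 kg.
- *Assumption:* a fraction f of BAE participants is recognized through the site, and recognition adds 2 kg of loss. For f = 0.10 to 0.50, bias = 2f = 0.2 to 1.0 kg, which is 0.2/4.7 = 4% to 1.0/4.7 = 21% of the planned difference.
- With no true effect, the chance of a result significantly favoring BAE is P(Z > 1.28 − bias/2.16). It is 10% with no bias, about 12% at 0.2 kg and about 21% at 1.0 kg.
- Counting rejections in both directions, the figures are 20% with no bias, 20.2% at 0.2 kg and 24.6% at 1.0 kg.

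Neither f nor the 2 kg comes from the documents. Recognition needs groin access, device use, an outward sign, someone noticing it and a correct inference. The upper end of f in particular has no documentary basis.

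**The case against.** The strongest opposing case is the third reading in step 2: one common rule, summarized loosely in the embolization text. The all-participants sentence supports it, and the simulation script may already settle closure and dressing. This stands as a possibility. It cannot be confirmed from the documents, and it would still leave wording to clarify.

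A reader might infer something stronger: that a visible closure device appears in the BAE arm only and so discloses allocation. The documents do not support that.

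- Controls with wrist access are themselves given a compression device.
- The embolization text does not say what the closure device is or whether it leaves any external sign. No text says that a mark lasts to the 1-week examination or beyond.
- Manual compression is also allowed after embolization, so its use would not identify sham. A groin device would be informative only to someone who knew that controls never receive one.
- Every participant has a skin nick.

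A reader might also infer that holding and rest times must be identical in both arms. The documents do not support that either. One arm has arterial access with a sheath and the other a skin nick, and Protocol 2.3.1 lists access-site bleeding and hematoma as risks. Those times are clinical matters for the investigators. Matching closure and dressing also cannot remove every difference between a sheath puncture and a nick. It removes only the avoidable difference that the wording permits.

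**Conclusion.** The point holds in limited form. For groin access the two closure texts in 6.1.1 do not agree, or at least are not shown to agree. As written, they permit a device after embolization that the control-arm text does not provide. No text requires the observable site to match or to be concealed from participants and blinded examiners. The access site could therefore give a clue to allocation. Disclosure is not shown.

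The size of any bias cannot be derived. The shift of 0.2 to 1.0 kg, with the chance of a false result favoring BAE rising from 10% to about 12–21%, rests wholly on the assumed recognition rate and 2 kg effect, and is an illustration only. The conclusion also depends on the simulation script, which is not in the documents, not already dealing with closure. This is a cheap improvement to the blinding, not a flaw that undermines the design.

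**What to change.** 1. Reconcile the two closure texts in 6.1.1 separately for wrist and groin, and state which arms each statement covers.
2. Require that what remains externally observable afterwards (device, dressing) not differ by arm, and add a matching line to the simulated-procedure script.
3. Record the closure method on the eCRF completed by the unblinded team member, who under 6.3 already enters procedure details there, so that departures can be counted by arm.

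The hemostasis method and the holding and rest times are left to the investigators. The cost is one reconciled paragraph, one added script line, one eCRF item and slightly less operator freedom in how the site is dressed. Sample size and analysis do not change.
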